12.6 Sample Size

12.6.1 Accrual estimates

Ten patients will be recruited prospectively. This is a pilot study. Ample time has been allotted for patient recruitment, and ten is a very feasible number so no shortage is expected. In the unlikely event that there is difficulty in recruiting a sufficient number of patients at Stanford Hospital, additional recruitment efforts at affiliated Stanford sites will be considered, if approved.

12.6.2 Sample size justification

This is a pilot study. This initial pilot group may provide the basis for proceeding to a prospective randomized-controlled trial thereafter.

12.6.3 Effect size justification

The most extensive study on rapid breast expansion post-mastectomy with expander implants emanates from Memorial Sloan-Kettering Cancer Center and includes 370 breast reconstructions in 314 patients. Mean time until last in-office expansion was reported as 6.6 weeks postoperatively³. Among the most highly-cited papers on conventional 2-staged implant-based breast reconstruction complications also comes from Memorial Sloan-Kettering Cancer Center and incorporates data on 1522 breast reconstructions in 1221 patients. This paper describes an overall complication rate of 5.6% for the stage 1 breast tissue expander insertion procedure and expansion process in nonradiated patients, which is identical to our study population characteristics. Confidence intervals not applicable to these 2 studies. These studies provide the ideal baseline to compare to as they include the same target population from a well-respected cancer center and high number of patients.

12.7 Criteria for future studies

As a pilot study, the criteria for success that would justify a fully powered study include: time to expansion (primary outcome) faster than described for the conventional technique in the literature (p<.05) as well as an incidence of complications comparable to that reported for conventional techniques in the literature. Lastly, acceptability by patients (based on the aforementioned surveys) will be taken into account.

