10.3 Secondary outcome measure: incidence of complications

- 10.3.1 This outcome will be measured on all subjects.
- 10.3.2 Defined as complications associated with tissue expansion process, including expander extrusion, wound breakdown, infection, and/or device malfunction.
- 10.3.3 Outcome will be measured by assessment of these patients at postoperative clinic visits for these complications.
- 10.3.4 Measurement time points will be at postoperative clinic visits, which will occur at weekly intervals during the expansion process. Follow-up will be approximately 12 months.

10.3.5 Response is not the primary outcome.

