12.5.2 Analysis Plan

Survey data for secondary outcomes 10.2 and 10.4, as described in previous sections, will be tabulated. Secondary outcome 10.3 will be analyzed with Student's t-test in order to compare with complication rates reported in the literature for conventional 2-staged IBR.

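### Section 12.7 requires a complication rate comparable to the published 5.6%; ten patients cannot show this, and because the word is undefined the chance of passing at a true rate of 20% runs from 11% to 97%

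*Combined protocol and SAP*

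**What the plan says.** Section 12.7 sets out what would justify a fully powered study: a shorter time to expansion than the literature reports, at p<.05; "an incidence of complications comparable to that reported for conventional techniques in the literature"; and patient acceptability, which is to be weighed without a threshold. No significance level, margin, maximum count or confidence limit goes with the complication criterion.

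The reference comes from 12.6.3: "This paper describes an overall complication rate of 5.6% for the stage 1 breast tissue expander insertion procedure", in nonradiated patients. That section gives the size of the series as 1522 reconstructions in 1221 patients and does not say which of the two is the denominator.

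On sample size, 12.6.1 says "Ten patients will be recruited prospectively", and 12.6.2 adds only that this is a pilot: "This initial pilot group may provide the basis for proceeding to a prospective randomized-controlled trial thereafter".

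The one planned analysis is in 12.5.2: "Secondary outcome 10.3 will be analyzed with Student's t-test in order to compare with complication rates reported in the literature". Section 10.3 defines the outcome as complications of the expansion process, "including expander extrusion, wound breakdown, infection, and/or device malfunction". No interval for the trial's own rate is planned.

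Section 4.2 separately says that the study will stop if complications rise above the rates reported for standard expander-implant reconstruction, again with no count or margin.

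**The concern.** A claim that two rates are comparable needs data that rule out a materially higher rate. The plan has only a test for a difference, in ten patients. If a non-significant result is taken to meet the criterion, lack of evidence is being read as evidence of similarity.

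The criterion also helps decide whether more patients receive the device in a randomised trial. With the term undefined, the same count can be called a pass or a fail, and that choice can be made after the data are seen.

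**Working it through.** **Inputs.** n = 10 patients (12.6.1); reference rate p0 = 0.056 (12.6.3); Student's t-test against the literature rate (12.5.2). The plan gives no precision or power calculation, so there is no figure of its own to reproduce. Assumptions: one independent yes/no outcome per patient, complete follow-up, and 5.6% treated as a fixed value.

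**Step 1: what ten patients can exclude.** For 0/n the exact upper limit is 1 − α^(1/n).

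- One-sided 95%: 1 − 0.05^(1/10) = 25.9%, and 25.9/5.6 = 4.6 times the reference.
- Two-sided 95%: 1 − 0.025^(1/10) = 30.8%, and 30.8/5.6 = 5.5 times the reference.
- For 1/10 the two-sided Clopper-Pearson interval is 0.3% to 44.5%.
- If all ten women had bilateral surgery and breasts were counted as independent, 0/20 would still give 13.9% (one-sided) or 16.8% (two-sided).

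So the best possible result does not exclude a rate several times the reference, however the term is read.

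**Step 2: which counts pass under each reading.**

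*Reading A: not significantly different on the 12.5.2 t-test, two-sided 0.05.* For x events in ten 0/1 values the standard error is √(x(10 − x))/30, and t = (x/10 − 0.056)/SE on 9 degrees of freedom.

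| x | t | p |
|---|---|---|
| 0 | none (zero variance) | none |
| 1 | 0.044/0.100 = 0.44 | 0.67 |
| 2 | 0.144/0.133 = 1.08 | 0.31 |
| 3 | 0.244/0.153 = 1.60 | 0.14 |
| 4 | 0.344/0.163 = 2.11 | 0.064 |
| 5 | 0.444/0.167 = 2.66 | 0.026 |

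Counting 0/10 as a pass, up to 4/10 passes. On a one-sided 0.05 test 4/10 gives p = 0.032, so up to 3/10 passes.

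*Reading B: not significantly different on an exact binomial test.* P(X ≥ 2 | 0.056) = 0.105 and P(X ≥ 3 | 0.056) = 0.016, so up to 2/10 passes.

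*Reading C: observed rate not above 5.6%.* One event is already 10%, so only 0/10 passes.

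**Step 3: probability of passing**, from the binomial with n = 10. A maximum of one event is added because it is a natural pre-set count.

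| True rate | A (≤4) | B (≤2) | ≤1 | C (0) |
|---|---|---|---|---|
| 5.6% | >99.9% | 98% | 90% | 56% |
| 11.2% (2×) | 99.7% | 91% | 69% | 31% |
| 16.8% (3×) | 98% | 77% | 48% | 16% |
| 20% | 97% | 68% | 38% | 11% |
| 30% | 85% | 38% | 15% | 3% |

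Two cells by hand: at 5.6%, P(0) = 0.944^10 = 0.562, so reading C fails an equally safe device 1 − 0.562 = 44% of the time. At 20%, P(0) + P(1) = 0.107 + 0.268 = 0.376.

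**The case against.** The best defence is that this is a declared pilot, complications are a secondary outcome, and the criterion only opens the way to a larger trial in which safety would be compared properly. Section 12.7 also weighs time to expansion and acceptability, so complications do not settle the decision alone. This stands, and it limits the severity. It does not rescue the criterion: a pilot can report a count and apply a cut-off, but it cannot support a statement of comparability with 5.6%.

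A reader might infer that the safety criterion is close to automatic, and that a device with three times the complications would usually be passed. The documents do not establish this. Section 12.7 attaches p<.05 to time to expansion only, and 12.5.2 does not say that its t-test decides the criterion. The inference holds under readings A and B. With at most one event allowed, a tripled rate passes 48% of the time, and under reading C only 16%. The wording of 4.2 leans towards reading C, where the main error is the opposite one: rejecting a device that is as safe as the reference.

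A reader might also take "Confidence intervals not applicable to these 2 studies" in 12.6.3 as ruling out intervals in this trial. It refers to the two cited series. The gap is that no interval is planned for the trial's own rate.

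**Conclusion.** The point holds in this form: the criterion claims something that ten patients cannot show, and it is not defined well enough to be applied the same way by two people. At the reference rate the chance of passing ranges from 56% to over 99.9% by reading; at a true 20% it ranges from 11% to 97%. The criterion may therefore be nearly automatic or close to a coin toss, and the plan does not say which.

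The limits in step 1 do not depend on the reading; the pass probabilities do. All figures rest on the assumptions listed with the inputs. Two further matters affect whether 5.6% is the right yardstick at all: its denominator is not stated, while bilateral cases are eligible under 3.1.1, and the protocol does not say whether it counts the same events as 10.3, which includes device malfunction.

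Severity is moderate.

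**What to change.** 1. In 12.5.2, replace the t-test for complications with x/n and the exact (Clopper-Pearson) 95% confidence interval. State the unit (patient or breast) and the event definition, both matched to the 5.6% reference. If breasts are the unit, two breasts in one woman are not independent and a simple exact interval would be too narrow.

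2. In 12.7, replace the comparability requirement with wording such as: *Complications will be reported as x/n with an exact 95% confidence interval. This pilot does not establish comparability with the published rate; that question is left to the randomised trial. Proceeding requires no more than k events.*

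3. Fix k before any outcome data are seen and print its pass probabilities beside it. For ten patients, at most 1 passes 90% of the time at a true 5.6% and 38% at 20%; at most 2 passes 98% and 68%. The investigators should choose k knowing that the looser count still passes a true 20% about two times in three.

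4. Reconcile 12.7 with 4.2. Read literally, a single event in ten (10%) is above 5.6% and would meet the termination wording, while either count above would allow the programme to proceed. The two sections must agree; this review does not propose the stopping rule.

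The sentence on confidence intervals in 12.6.3 can stay.

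The cost is protocol wording, with no extra patients or data. The stated claim on safety becomes less favourable, which is all that ten patients can support.

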APPENDIX A: Participant Eligibility Checklist

A Participant Eligibility Checklist must be completed in its entirety for each subject prior to registration. The completed, signed, and dated checklist must be retained in the patient's study file and the study's Regulatory Binder.

The study coordinator, treating physician and an independent reviewer must verify that the participant's eligibility is accurate, complete, and legible in source records. A description of the eligibility verification process should be included in the EPIC or other Electronic Medical Record progress note.

The following is an **example** of a Participant Eligibility checklist template. Modify this checklist to fit your study and include it in the appendix section of your protocol document. The protocol-specific checklist is **required** by the SRC and must be approved by the IRB.

Protocol Title:	
	Applying New Device Technologies for Tissue
	Expander/Implant-Based Breast Reconstruction
Protocol Number:	36748
Principal Investigator:	[name]

II Subject Information.

11. Subj	ect information:			
	Subject Name/ID:			
	Gender: Male Female			
III. Stud	dy Information:			
SRC Approved IRB Approved Contract signed				

IV. Inclusion/Exclusion Criteria

	Inclusion Criteria (From IRB approved protocol)	Yes	No	Supporting Documentation*
1.	Diagnosis of breast cancer or reason for prophylactic mastectomy (e.g., BRCA mutation and/or strong family history of breast cancer), both unilateral and bilateral mastectomy.			
2.	No prior breast surgery (excluding biopsy and lumpectomy) or breast radiation			
3.	Women age 18 years or older, no race- ethnic restrictions			
4.	Ability to understand and willingness to sign written informed consent document			

	5. No life expectancy restrictions							
	6. ECOG or Karnofsky Performance Status will not be employed							
	7. No requirements for organ and marrow function							
	Exclusion Criteria (From IRB approved protocol)							
	1. Recent steroid use							
	No major medical comorbidities (defined as ASA III or greater)							
	3. No connective tissue disorder							
	Prior breast surgery, excluding biopsy and lumpectomy							
	5. History of or plan for breast radiation							
	6. Pregnant and nursing patients							
	7. No restrictions regarding use of other Investigational Agents							
	8. No exclusion criteria related to history of allergic reactions							
